#### **1. Abstract**

Due to an organ shortage crisis, many individuals with end-stage renal disease will die or become too sick to undergo transplantation before receiving a kidney transplant. At the same time, many high quality kidneys from hepatitis C infected (HCV+) donors are discarded every year because there is no HCV+ waitlist candidate available to accept the organ. New HCV therapies are highly effective and well tolerated, with cure rates of nearly 100%. This study is a single center, open-label, pilot interventional trial of glecaprevir/pibrentasvir for 10 HCV- nonviremic recipients of kidneys from HCV-infected deceased donors at Johns Hopkins Hospital (JHH).

The primary hypothesis is that prophylactic treatment with glecaprevir/pibrentasvir before and after transplant will prevent the establishment of HCV infection in the recipients of kidneys from HCV-infected deceased donors. The safety hypothesis is that grade 3-4 AE related to G-P will occur in  $\leq 10\%$  of participants. Based on the success of preliminary studies, the objective of this study is to evaluate the safety and efficacy of two weeks of glecaprevir/pibrentasvir as prophylactic therapy for HCV D+/R- kidney transplantation.

#### **2. Objectives**

##### Primary objectives:

The primary objectives of this study are to evaluate the safety and efficacy of glecaprevir 300 mg/pibrentasvir 120 mg (G-P) treatment in HCV-nonviremic transplant recipients (HCV R-) of a kidney from an HCV-infected deceased donor (HCV D+). G-P will be administered on-call to the operating room (OR) for the kidney transplant procedure and continued for 2 weeks after the kidney transplant.

- The primary efficacy outcome will be the proportion of HCV D+/R- renal transplant recipients with undetectable HCV plasma RNA at 12 weeks after treatment (14 weeks after kidney transplant).
- The primary safety outcome will be the incidence of adverse events (AE) related to G-P.

##### Secondary outcomes:

- Proportion of kidney transplant recipients who have undetectable HCV plasma RNA at 1, 2, 4 and 12 weeks after discontinuation of therapy.
- Proportion of kidney transplant recipients who become reactive for HCV antibodies following transplant.
- Kidney allograft function at 6 and 12 months and 24 months following transplantation, including creatinine, glomerular filtration rate and assessment of protein in the urine.

Date: September 26, 2023

Principal Investigator: [name]

Application Number: IRB00237097

### 3. Background

As of March 20, 2020, there are 94,874 individuals awaiting a life-saving kidney transplant in the United States; however, due to a shortage of donor organs, only 23,400 kidney transplants were performed in 2019 [1]. Waiting times in the United States for a kidney transplant average 5 years and up to half of all individuals on the waiting list will die or become too sick to undergo the procedure. Mortality on the kidney transplant waiting list is 6% per year with significant variation depending on patient characteristics and the geographic location where the patient lives. The death rate on the kidney waiting list for older individuals and for individuals with diabetes is approximately 10% per year. Therefore, a patient over 60 years of age with an estimated waitlist time of five years for a kidney has a 50% chance of death before a kidney becomes available [2,3].

Kidneys from hepatitis C-infected (HCV+) donors are currently underutilized. From 2014-16, over 40% of kidneys from HCV+ deceased donors were discarded, compared to 18% of kidneys from HCV-uninfected (HCV-) donors. Many of these HCV+ organs are of excellent quality, but are frequently discarded due to a lack of hepatitis C-infected waitlist candidates [4].

One strategy to expand the kidney donor pool is to transplant HCV+ donor kidneys into HCV- recipients (HCV D+/R- transplant) in combination with direct-acting antivirals (DAAs) to treat HCV. In 2016, we performed the first study in the world using this strategy at Hopkins (EXPANDER: An open-label study to determine the efficacy and safety of fixed-dose grazoprevir/elbasvir treatment in hepatitis C uninfected recipients of renal transplants from hepatitis C infected deceased donors. IRB 00089751; NCT# 02781649). This study was a pilot trial of this approach in 10 HCV-uninfected kidney transplant recipients using DAAs as pre- and post-transplant prophylaxis. Depending on the donor HCV genotype, the DAAs grazoprevir/elbasvir with or without sofosbuvir were used. In this trial, HCV- recipients were given the first dose of DAAs just prior to the transplant procedure and were subsequently treated with standard treatment durations of 12-16 weeks (depending on donor HCV genotype) of DAAs after transplant. The length of DAA therapy was based on the kidney donor's HCV genotype. Ten HCV D+/R- transplants were performed at Johns Hopkins and this approach was successful in preventing chronic hepatitis C infection in all 10 recipients. The DAAs were well tolerated and there were no grade 3 or grade 4 serious adverse events noted [5].

In addition to the study described above, a similar study at the University of Pennsylvania treated 10 HCV negative participants receiving an HCV+ donor kidney with elbasvir-grazoprevir for 12 weeks and reported SVR in all 10 participants at week 12 post treatment [6]. In contrast to the Hopkins EXPANDER study where a prophylactic strategy was used to treat donor-derived hepatitis C infection in recipients, the Penn study used a pre-emptive approach, waiting for recipients to have detectable HCV RNA in the blood prior to initiating DAA therapy. In that trial, 10/10 patients had detectable HCV RNA in peripheral blood by day 3. All patients were cured with 12 weeks of DAA therapy [6].

An important finding in the EXPANDER study was the short duration and low level of viremia observed in transplant recipients when DAA treatment was initiated just prior to the transplant procedure. In contrast, the U Penn group observed much higher levels of persistent hepatitis C viremia in their study where DAA therapy was delayed for several days. We hypothesized that shorter duration DAA therapy would be successful and tested this hypothesis in a recently completed study (Renal transplants in hepatitis C negative recipients with nucleic acid positive donors, IRB00174409; NCT#03627299). In this study we used the once daily, fixed-dose combination of the NS3/4A protease inhibitor glecaprevir

Date: September 26, 2023

Principal Investigator: [name]

Application Number: IRB00237097

(G) and the NS5A inhibitor pibrentasvir (P) as the DAA. This medication was newly approved for the treatment of all hepatitis C genotypes (1-6) and is not metabolized by the kidneys. Thus, it was felt to be the best regimen to use as pre- and post-exposure prophylaxis in the early post-kidney transplant period [7].

In this recently completed study with 4 weeks of DAA treatment, all ten recipients completed 4 weeks of G-P following transplantation as well as 12 weeks of follow-up after completing DAA therapy. All 10 patients cleared hepatitis C and remained HCV negative throughout the follow-up period. All 10 patients had excellent kidney graft function through 6 months of follow-up; however, one patient did lose kidney transplant function approximately 8 months after transplantation due to a late renal vein thrombosis that was unrelated to hepatitis C or to DAA treatment. Of note, only 5 of 10 recipients showed any evidence of hepatitis C viremia during the early post-op period and the highest quantifiable viral loads observed were on postoperative day 1 in three patients (post-operative day 1 hepatitis C viral loads: 161, 153, and 87 IU/ml). All recipients were clear of hepatitis C after the first week following transplantation [8].

Based on the success of these preliminary studies, the objective of our current study is to evaluate the safety and efficacy of two weeks of glecaprevir/pibrentasvir as prophylaxis for HCV D+/R- kidney transplantation.

#### 4. Study Procedures

This is a single center, open-label, pilot trial of glecaprevir/pibrentasvir for 10 HCV- nonviremic recipients (R-) of kidneys from HCV-infected deceased donors (HCV D+) at Johns Hopkins Hospital (JHH). Individuals who meet the inclusion criteria will be offered enrollment. Informed consent will be obtained by a physician on the study team and those who provide informed consent will be enrolled. All participants will be initiated on oral, once-daily, fixed-dose G-P starting on call to the operating room for the kidney transplant.

**Screening Phase:** HCV RNA negative individuals on the kidney transplant waiting list at Johns Hopkins Hospital (JHH) will be recruited and screened for eligibility. Individuals who are interested in the study will give informed consent. We will approach HCV negative individuals on the deceased donor kidney transplant waitlist who meet the recipient inclusion criteria. Currently there are over 500 individuals meeting these criteria at JHH. At JHH, approximately 50% of current waitlist candidates will accept Infectious Risk Donors (IRDs). We anticipate a lower acceptance rate of HCV+ deceased donors and estimate a 20% participation rate. Thus, we estimate having a pool of at least 50 eligible screened participants and our consenting target is 25, with 10 subjects enrolled and transplanted. Once a patient signs a consent form, a unique baseline number will be assigned for identification purposes. Prior to transplantation, data on demographics (age, sex, race, etc.), medical history, social history, and renal biopsy diagnosis (when available) will be collected.

We estimate 2 months for screening and consenting a pool of 20 eligible patients. At JH the approximate wait time for an HCV+ deceased donor is approximately 6 months. Therefore, we anticipate an average of one HCV D+/R- transplant per month, with an accrual period of 12 months. Total study duration will therefore be 24 months.

**Accrual Objective:** 10 participants **Accrual Period:** 12 months **Total Study Duration:** 24 months  
Long-term follow-up at 2-years: 24 months

Date: September 26, 2023

Principal Investigator: [name]

Application Number: IRB00237097

[figure not shown]
**HCV+ Donor Identification:** Those who provide informed consent for the study will be listed in the United Network for Organ Sharing (UNOS) with a status of “willing to accept an HCV+ organ”. The JHH transplant team will then receive HCV+ donor kidney offers for the study participant from Organ Procurement Organizations (OPOs). If an HCV+ donor who meets the inclusion criteria is identified, the study participants will be offered the organ and, if they accept, they will become an active treatment participant. A donor blood sample will be obtained from the OPO for the purposes of this study. Currently, offering OPOs only perform a qualitative HCV RNA by nucleic acid testing. HCV quantification and genotyping are not performed on donors, and no FDA approved assays exist for this indication in organ donors. Donor HCV RNA quantification and HCV genotyping will be performed in parallel with the transplantation and initiation of treatment. The OPO will ship a donor blood sample to JHH for HCV genotyping and HCV RNA quantification. Plasma will be banked for future resistance testing if needed.

Date: September 26, 2023

Principal Investigator: [name]

Application Number: IRB00237097

## **Screening, enrollment and treatment (Figure 1)**

Date: September 26, 2023

Principal Investigator: [name]

Application Number: IRB00237097

**Active Phase, Transplant and Treatment:** At the time of transplant admission, the kidney recipient will undergo the standard pre-operative work-up, including laboratory testing, chest X-ray, EKG, and urinalysis (if applicable). In addition, a sample for baseline HCV serology will be drawn if not performed within the past 12 months. Donor and recipient crossmatch will be performed using T cell and B cell complement-dependent cytotoxicity crossmatch. In addition, quantitative assessment for the presence of donor specific antibody will be performed by solid phase assay (Luminex) and confirmed to be below a flow positive level. Once a recipient is deemed appropriate to undergo the kidney transplant procedure and the HCV+ donor organ has been examined and found to be acceptable for transplant, the recipient will be called to the operating room. The initial dose of G-P will be administered to the recipient when called to the operating room (see treatment strategy below).

The deceased donor kidney transplant procedure will be performed in the standard manner under general anesthesia with appropriate monitoring lines. Intraoperative medications will include intravenous cefazolin, heparin, mannitol, and furosemide. Anesthetic medications include inhalational agents, muscle relaxant, and narcotic pain medication. Other standard medications will be administered as well. Induction immunosuppression administered in the operating room will consist of intravenous Solumedrol (500 mg) and intravenous rabbit anti-thymocyte globulin (1.5 mg/kg) (Thymoglobulin, Genzyme). During the transplant operation, a surgical drain(s), ureteral stent, and urinary catheter will be placed.

Postoperative care will be performed in the standard manner in a monitored, step-down intensive care unit setting. Ongoing induction immunosuppression with daily Solumedrol and Thymoglobulin for three post-operative doses each will be administered per JHH protocol. In addition, maintenance immunosuppressive therapy consisting of tacrolimus, mycophenolate mofetil, and prednisone will be initiated. Tacrolimus dosing will be adjusted to obtain a serum trough concentration between 7-10 ng/ml for the first three months postoperatively and then 6-8 ng/ml beyond three months. Mycophenolate mofetil will be administered in divided doses for a total dose of 1000-2000 mg daily. Prednisone will be initiated at a dose of 20 mg daily once the initial course of Solumedrol is completed and gradually tapered to 5 mg daily by 6-12 weeks.

Standard post-transplant prophylaxis strategies will be used in subjects for the prevention of opportunistic infections. These include trimethoprim-sulfamethoxazole (Bactrim) for pneumocystis pneumonia prophylaxis, valganciclovir for cytomegalovirus infection in cases of CMV seropositive donors and/or recipients, and fluconazole for fungal prophylaxis.

Additional postoperative care will be performed in the standard manner and include intravenous fluids to replace urine output for the first 24 hours postoperatively. Early mobilization and ambulation will be encouraged. Diet advancement will start with clear liquids several hours after surgery and progress to a regular diet by approximately 24 hours after surgery. The urinary catheter will remain in place for 3-7 days after surgery, depending on the condition of the patient's bladder at the time of the transplant operation. Surgical drain(s) placed at the time of the transplant procedure remain(s) in place until daily output is below 50 ml per day. The ureteral stent is removed by cystoscopy approximately 4-8 weeks after surgery.

Discharge from the hospital is typically between 5 and 10 days postoperatively, once renal transplant function is established, the patient is tolerating a regular diet, having normal bowel and bladder function, and has a satisfactory understanding of post-transplant care. During the hospitalization, teaching of

[figure not shown]
transplant medications and planned follow-up will occur on several occasions. Included in this teaching will be the medication and follow-up labs and visits related to the study protocol.

**Treatment Strategy:** The study participant will be admitted to the hospital and undergo standard recipient admission work-up. Once this work-up is completed, crossmatch results are available, and relevant donor kidney information is available (including examination of the kidney in the operating room to confirm anatomic suitability for transplantation), the first dose of G-P will be administered when the recipient is called to the operating room (typically 1-3 hours prior to start of surgery). Post-transplant, G-P will be continued daily at 10 AM to correspond with the inpatient daily dosing nurse medication administration. To ensure timely delivery daily at 10 AM, the first dose post-operatively may occur before, but not after, 36 hours. For example, if the participant received the first dose pre-transplant at 2:00 PM, the second dose will take place 20 hours later on post-operative day #1 at 10:00 AM. Most renal transplant recipients are extubated in the operating room and able to take oral medications within eight hours after the transplant procedure. During the hospitalization, G-P will be given once daily.

**Visit Schedule:** Study visits will occur at days 0, 1, 4, 7, treatment week 2, and follow-up weeks (FW) 1, 2, 4 and 12 for all participants. Post-transplant data collection will include the laboratory data indicated in the Schedule of Events (Table 1). We will also collect immunosuppression regimen, tacrolimus trough, creatinine level, acquisition of opportunistic infections, graft survival and patient survival. Allograft biopsies will be performed if there is concern for rejection or other causes of graft dysfunction. Allograft biopsies will be classified by the Banff criteria.

**Year 2 Long-Term Follow-Up:** As of August 18, 2022, all 10 subjects were accrued and completed the 1-year study. The study team proposes a minimal risk long-term follow-up in order to capture survival, rejection, graft failure, and eGFR data from the EMR at 2-years post-transplant. We will call previously enrolled subjects that consented for Future Contact to gauge their interest and obtain oral consent for the collection and use of their health information through the 24 month timepoint. No procedures are involved; chart review only. We will use an oral consent script.

## **Treatment and follow-up strategy (Figure 2)**

## HCV Plasma RNA Measurement

Date: September 26, 2023

Principal Investigator: [name]

Application Number: IRB00237097

TD = treatment day, TW = treatment week, FW = follow-up week

### Schedule of Events (Table 1)

	Baseline	POD 1, 4, 7	TW 2	FW 1	FW 2	FW 4	FW 12
Donor HCV genotype a	X						
Donor HCV quant RNA b	X						
Recipient HCV RNA b	X	X	X	X	X	X	X
Recipient HCV Serology c	X						X
Recipient Hematology d	X	X	X	X	X	X	X
Recipient Chemistry e	X	X	X	X	X	X	X
Recipient Physical exam	X		X		X	X	X

POD post-operative day; TW treatment week; FW follow up week

aHCV genotype and subtype will be determined

bHCV RNA will be measured using an FDA approved assay in a CLIA certified lab.

cHCV antibody testing using an FDA approved assay in a CLIA certified lab.

dHematocrit, Hemoglobin, platelet count, red blood cell count, white blood cell count– standard of care

eAlanine aminotransferase, aspartate aminotransferase, albumin, alkaline phosphatase, creatinine, total bilirubin, glucose, potassium, and sodium– standard of care

#### **Adverse Event Reporting:** Adverse event reporting will follow the requirements outlined below.

Adverse events will also be recorded and tracked in a safety monitoring database by the investigators. Serious adverse events will be reported to the Institutional Review Board at Johns Hopkins University according to IRB guidelines and to the sponsor.

Participants undergoing solid organ transplantation will be expected to have frequent adverse events (AEs) related to the organ transplant surgery and immunosuppressants, which are not the subject of this protocol. This protocol focuses on the use of G-P. Grade 3 and Grade 4 AEs and SAEs related to the use of G-P will be collected.

All Grade 3 or 4 AEs and all SAEs will be reviewed by the principal investigator as they occur in a timely manner. All serious adverse events (SAEs) will be reported to the IRB. Grade 3 or higher AEs that are possibly or definitely related to G-P will be reported to the IRB.

#### Adverse Event (AE) Definition

Any untoward or unfavorable medical occurrence associated with the participant's participation in the research, whether or not considered related to the participant's participation in the research (modified from the definition of adverse events in the 1996 International Conference on Harmonization E-6 Guidelines for Good Clinical Practice) (from OHRP "Guidance on Reviewing and Reporting Unanticipated Problems Involving Risks to Participants or Others and Adverse Events (1/15/07)" <http://www.hhs.gov/ohrp/policy/addevntguid.html#Q2> )

For this study, an adverse event will include any untoward or unfavorable medical occurrence associated with, but not limited to:

1. Worsening (change in nature, severity or frequency) of conditions present at the onset of the study
2. Intercurrent illnesses
3. Infections

Date: September 26, 2023

Principal Investigator: [name]

Application Number: IRB00237097

4. Abnormal laboratory values (significant shifts from baseline within the range of normal that the investigator considers to be clinically important)
5. Clinically significant abnormalities in physical examination, vital signs, weight, and/or tests and procedures
6. Surgical complications

#### Serious Adverse Event (SAE) Definition

An adverse event or suspected adverse reaction is considered “serious” if, in the view of the investigator it results in any of the following outcomes (21 CFR 312.32(a)):

1. Death
2. A life-threatening event: An AE or SAR is considered “life-threatening” if, in the view of the investigator, its occurrence places the participant at immediate risk of death. It does not include an AE or SAR that, had it occurred in a more severe form, might have caused death.
3. Inpatient hospitalization or prolongation of existing hospitalization
4. Persistent or significant incapacity or substantial disruption of the ability to conduct normal life functions
5. Congenital anomaly or birth defect
6. Important medical events that may not result in death, be life threatening, or require hospitalization may be considered serious when, based upon appropriate medical judgment, they may jeopardize the participant and may require medical or surgical intervention to prevent one of the outcomes listed above

#### **Grading and Attribution of Adverse Events**

##### Grading Criteria:

AEs will be graded according to the criteria set forth in the National Cancer Institute’s Common Terminology Criteria for Adverse Events (CTCAE) version 4.0. This document (referred to herein as the NCI-CTCAE manual) provides a common language to describe levels of severity, to analyze and interpret data, and to articulate the clinical significance of all adverse events.

Adverse events will be graded on a scale from 1 to 5 according to the following standards in the NCI-CTCAE manual:

- Grade 1 = mild adverse event.
- Grade 2 = moderate adverse event.
- Grade 3 = severe and undesirable adverse event.
- Grade 4 = life-threatening or disabling adverse event.
- Grade 5 = death.

Events grade 3 or higher that are possibly or definitely related to study procedures or intervention will be collected on AE case report.

##### Attribution Definitions:

The relationship, or attribution, of an adverse event to the study intervention or study procedures will initially be determined by the investigator. For additional information and a printable version of the NCI-CTCAE manual, consult the NCI-CTCAE web site: <http://ctep.cancer.gov/reporting/ctc.html>.

**Unrelated:** The adverse event is clearly not related; there is insufficient evidence to suggest a causal relationship.

**Possibly Related:** The adverse event has a reasonable possibility to be related; there is evidence to suggest a causal relationship.

**Definitely Related:** The adverse event is clearly related.

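### The definition of an unrelated event includes insufficient evidence of causality and no category exists for uncertain cause, so grade 3+ events of uncertain cause can drop out of the primary safety count

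*Combined protocol and SAP*

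**What the plan says.** All references are to the combined protocol and SAP.

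- **Outcome.** Section 2, Primary objectives: "The primary safety outcome will be the incidence of adverse events (AE) related to G-P". The Abstract adds a threshold: "The safety hypothesis is that grade 3-4 AE related to G-P will occur in" at most 10% of participants.
- **Attribution.** Section 4, Attribution Definitions, has three categories. The lowest, *Unrelated*, is worded as "The adverse event is clearly not related; there is insufficient evidence to suggest a causal relationship". For the middle one, *Possibly Related*, the wording is "The adverse event has a reasonable possibility to be related; there is evidence to suggest a causal relationship". The third, *Definitely Related*, needs a clear link. Who makes the call is also stated: the relationship "will initially be determined by the investigator".
- **Case report.** Section 4, Grading Criteria: "Events grade 3 or higher that are possibly or definitely related to study procedures or intervention will be collected on AE case report".
- **Background events.** Section 4, Adverse Event Reporting: "Participants undergoing solid organ transplantation will be expected to have frequent adverse events (AEs) related to the organ transplant surgery and immunosuppressants".
- **Wider capture.** The same Adverse Event Reporting text mentions a safety monitoring database for adverse events and principal-investigator review of all grade 3 or 4 AEs and all SAEs, neither limited by relatedness. Collection Period gathers SAEs from first dose, also without a relatedness condition. Adverse Event Reporting, Recording Adverse Events and section 8.C send all SAEs to the IRB.

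**The concern.** A lack of evidence for a causal link does not show that there is none, yet the definition of *Unrelated* treats the two as one state. This matters because attribution decides the numerator of the primary safety outcome, and under the Grading Criteria it also decides what goes on the AE case report.

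The setting makes uncertain attribution likely. The plan itself expects many events from surgery and immunosuppression, so competing explanations will be common. The trial is open-label with no comparison group, and no independent adjudication of attribution is described. If truly related events are classed as unrelated, the reported incidence is too low. With 10 participants, very few such events could change whether the 10% threshold appears to be met.

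**Working it through.** **Step 1: the definitions side by side.**

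| Category | First clause | Evidence clause |
|---|---|---|
| Unrelated | a clear negative | evidence is insufficient |
| Possibly Related | a reasonable possibility | evidence points to a link |
| Definitely Related | a clear positive | none |

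Take an event for which G-P is a reasonable possibility but positive evidence is lacking. It meets the second clause of *Unrelated* but not the first. It meets the first clause of *Possibly Related* but not the second. It fits no category in full. The two evidence clauses mirror each other, so an investigator who decides on evidence will choose *Unrelated*. The wording permits that result but does not compel it. Recording Adverse Events and section 8.C use a further term, potentially related, which the definitions do not cover.

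**Step 2: where a grade 3 or higher event goes.**

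| Event | Primary count | Recording |
|---|---|---|
| Possibly or definitely related to G-P | in | AE case report |
| Classed unrelated, serious | out | collected as an SAE under Collection Period; sent to the IRB |
| Classed unrelated, non-serious | out | off the AE case report; reviewed by the principal investigator; perhaps in the safety database |

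The collection rules disagree. One sentence in Adverse Event Reporting limits collection to grade 3 and 4 AEs and SAEs related to G-P. Grading Criteria uses relation to study procedures or intervention. Collection Period gathers SAEs with no such limit. The database sentence states no grade, attribution field or analysis.

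**Step 3: the plan's own arithmetic.** The only computed figure, in Power/Sample Size, is 1 − 0.79^10 = 0.9053. It matches the stated 90.53% but concerns efficacy. The safety hypothesis has no calculation to reproduce.

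**Step 4: what the threshold means at n = 10.** 10% × 10 = 1 participant. Exact (Clopper-Pearson) 95% intervals:

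| Observed | Rate | Interval | At or below 10%? |
|---|---|---|---|
| 0/10 | 0% | 0% to 30.8% | yes |
| 1/10 | 10% | 0.25% to 44.5% | yes |
| 2/10 | 20% | 2.5% to 55.6% | no |

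**Step 5: sensitivity to misclassification.** The documents give no misclassification rate, so both inputs are assumptions: p is the true share of participants with a G-P-related grade 3-4 event, and m is the share of those participants lost from the count. Then q = p(1 − m), and

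P(at most 1 of 10) = (1 − q)^10 + 10q(1 − q)^9.

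For p = 20%, m = 0: 0.8^10 + 10 × 0.2 × 0.8^9 = 0.1074 + 0.2684 = 0.3758. For p = 20%, m = 50%: q = 0.1, giving 0.3487 + 0.3874 = 0.7361.

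| True rate p | m = 0 | m = 25% | m = 50% | m = 75% |
|---|---|---|---|---|
| 10% | 73.6% | 83.0% | 91.4% | 97.5% |
| 20% | 37.6% | 54.4% | 73.6% | 91.4% |
| 30% | 14.9% | 30.5% | 54.4% | 83.0% |

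At p = 20%, the expected observed rate falls to 15%, 10% and 5% as m goes from 25% to 50% to 75%. These figures show how sensitive the result is; they do not estimate what happened.

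**The case against.** A reader might infer that uncertain events are simply not collected and that the primary safety result is therefore biased downward. The documents do not support that.

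- **Collection.** SAEs are gathered and sent to the IRB whatever their attribution, all grade 3-4 AEs are reviewed, and a safety database is described. The clear gap is non-serious grade 3 or higher events classed as unrelated. This stands and narrows the point, but an SAE classed as unrelated still leaves the primary count.
- **Classification.** An uncertain event does not meet the clear-negative clause of *Unrelated*, and an investigator could choose *Possibly Related* on the strength of a reasonable possibility. This also stands: misclassification is permitted, not required. The alternative reading, that the event fits no category, is still a defect.
- **Direction of bias.** Downward bias needs truly related events to be misclassified. Many uncertain events after a transplant will be due to surgery or immunosuppression, and leaving those out is correct. Over-attribution of background events would push the rate up. Hence this is a risk of unknown size.
- **Decision rule.** The plan ties no formal test to 10%, and the intervals for 0/10, 1/10 and 2/10 all contain 10%. No result in that range settles the hypothesis, so what is at stake is how the observed rate is read against the threshold.
- **Later checking.** Reviewed events should be retrievable, and scheduled hematology and chemistry can be re-graded, so the loss is not beyond repair. However, all 10 participants had completed the 1-year study by August 18, 2022, so any re-attribution now is post hoc.

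**Conclusion.** The definition of *Unrelated* is internally inconsistent and no category covers uncertain cause. A grade 3 or higher event of uncertain cause can therefore leave the primary safety count and, if non-serious, the AE case report as well. The section 4 statements on what is collected conflict and must be reconciled.

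The size of any understatement cannot be derived from the documents. What can be said is that the threshold equals one participant, so reclassifying a single participant can move the observed rate from 20% to 10%. The Step 5 probabilities hold only under the assumed values of p and m, with participants independent and no upward misattribution. This is a cheap improvement that makes the primary safety result checkable, not evidence that the result is wrong.

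**What to change.** 1. In Attribution Definitions, delete the insufficient-evidence clause from *Unrelated* and state where events of uncertain cause are placed. Defining *Possibly Related* as anything that cannot be ruled out is one option, but without a comparator it could inflate the related count with transplant events, so the choice should be explicit.
2. Reconcile Adverse Event Reporting, Grading Criteria and Collection Period on what is collected, and replace or define the term potentially related.
3. Record every grade 3 or higher AE from first dose through follow-up week 12 with its attribution. For the 10 completed participants, use the grade 3-4 AEs and SAEs that the principal investigator was to review.
4. Report all-cause grade 3 or higher incidence beside G-P-related incidence, each with an exact interval. Keep the attributions made during the trial and label any re-attribution as post hoc.

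Cost: wording changes and a small amount of data entry for 10 people. The all-cause count will include transplant-related events, so it must be read beside the related count.
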